8.1 Required Accessories and Supplies

8.1.1 Accessories to be provided by the IR suite / cath lab

1. Introducer Sheath(s) - 7F or greater and of appropriate length. The sheath selected must reach the target site and allow for retraction to expose the infusion basket. A 75cm length or less straight tip sheath, e.g. Flexor® Raabe Guiding Sheath (Cook Medical, Inc.) or equivalent for femoral access is recommended for most. ***The sheath length must be long enough to reach the clot and must not exceed 75cm.*** A shorter sheath of appropriate length may be utilized for IJ access and the ***sheath used must be able to reach the clot.***
2. Ultrasound for ultrasound guided access *is required* for both IJ and CFV access.
3. Micropuncture kit for IJ and CFV venous access is required for both IJ and CFV access.
4. Guidewire - .018in x 300cm in length minimum (Hi-torque Steelcore® Peripheral Guide Wire Abbott Vascular or equivalent).
5. 7F Swan-Ganz catheter with 0.035in guidewire lumen (Arrow® or equivalent) or an angled pigtail catheter.
6. 3-way stopcock(s) – with Luer-lock connectors (2 for unilateral / 4 for bilateral procedures).
7. Infusion pump(s) and IV tubing for r-tPA infusion(s).
8. Heparinized saline for flushing.
9. 0.9% NaCl intravenous (IV) infusion bag 500cc for r-tPA pulse spray mixture.
10. Sterile water for injection, USP (Do not use bacteriostatic water, USP for injection) – for 2.2mg vial Cathflo™ Alteplase (r-tPA) mixture (Genentech, Inc., South San Francisco, CA).
11. r-tPA vial(s) for pulse sprays.
 - a. **Unilateral PE:** One (1) 2.2mg vial of Cathflo™ Alteplase (r-tPA) for pulse spray use.
 - b. **Bilateral PE:** Two (2) 2.2mg vials of Cathflo™ Alteplase (r-tPA) for pulse spray use.
12. 10cc syringes to administer pulse spray r-tPA
 - a. **Unilateral PE:** Two (2) 10cc syringes for injecting the pulse sprays.
 - b. **Bilateral PE:** Four (4) 10cc syringes for injecting the pulse sprays
13. Heparinized saline at 500 units/500cc .9% NaCl or 100 units/500cc .9% NaCl or .45% NaCl or other standard of care heparinized saline concentration, or normal saline without heparin intravenous (IV) pressure infusion bag(s) with transducer tubing if the BEC will be used to monitor PA pressures in the ICU.

14. r-tPA Infusion:

- a. **Unilateral PE:** Obtain three (3) 2.2mg vials of Cathflo™ Alteplase (r-tPA) for continuous infusion to be started in the IR suite / cath lab for a total of 5mg for one infusion. *Mixture requirements are in section 8.3.*
- b. **Bilateral PE:** Obtain five (5) 2.2mg vials of Cathflo™ Alteplase (r-tPA) for continuous infusion to be started in the IR suite / cath lab for a total of 5mg for each infusion for two infusions. *Mixture requirements are in section 8.3.*

8.1.2 Procedure Supplies Provided by the Sponsor

1. Bashir™ and Bashir™ S-B Endovascular Catheters

8.2 Baseline Hemodynamic Readings

The following readings will take place using the Swan-Ganz or angled pigtail catheter in the IR suite / cath lab prior to placement of the Bashir™ Endovascular Catheter(s).

1. PA Pressures measured using a Swan-Ganz catheter or angled pigtail: PAS / PAD / PA Mean
2. S_pO_2 – Pulse Oximeter Arterial Oxygen Saturation
3. S_vO_2 – Mixed Venous Oxygen Saturations (from tip of a pigtail catheter or Swan-Ganz Catheter PA port)
4. CO – Modified Fick Calculation
5. CI – Calculation

8.3 r-tPA Administration - Prepare Pulse Spray(s) and Infusion(s) prior to opening the Bashir Endovascular Catheter (BEC).**8.3.1 Reconstitution of r-tPA Pulse Spray Mixture**

1. Obtain a 2.2mg vial of r-tPA (1mg/ml) provided by the site.
2. Mix the lyophilized powdered r-tPA with 2.2ml sterile water for injection (as stated in the r-tPA information sheet) to obtain 1mg/ml. Do not use bacteriostatic sterile water for injection.
3. Aspirate exactly 1mg (1ml) into a 3cc syringe (for accuracy).
4. Inject 1.0mg (1ml) of r-tPA mixture into a 10cc syringe, and aspirate 0.9% NaCl to have a maximum of 10cc of diluent and drug mixture in the syringe.
5. Repeat step 1 through 4 above x 1.
6. This equals two (2) 10cc pulse spray doses (1.0mg/10cc in one 10cc syringes per pulse spray) with 1.0mg r-tPA per dose - Total of 2.0mg of r-tPA for unilateral PE).
7. If treating bilateral PE, repeat steps 1 through 5 above, for a total of 4.0mg, 2.0mg per PA. This equals four (4) 10cc pulse spray doses (1.0mg/10cc in one 10cc syringes per pulse spray).

Table 2. r-tPA Doses and Mixtures for Pulse Sprays and Infusions through the BEC

Pulse Sprays						
	No. of 2.2mg Cathflo™ r-tPA Vials Required	Diluent: Sterile Water for Injection	Total Diluent Required 0.9% NaCl	Total Dose per Syringe	Total Syringes for Pulse Sprays	Total Pulse Spray Dose
Unilateral PE	1	2.2ml per vial to have 1mg/ml	Total of 20cc including r-tPA	1.0mg in each 10cc syringe	Two 10cc syringes	2.0mg
Bilateral PE	2	2.2ml in 1 vial for 1mg/ml	Total of 40cc including r-tPA	1.0mg in each 10cc syringe	Four 10cc syringes	4.0mg

Infusion(s)				
	No. of 2.2mg Cathflo™ r-tPA Vials Required	Total Diluent Required 0.9% NaCl	Infusion Rate	Total Infusion Dose
Unilateral PE	3	500cc total including r-tPA mixture x 1 bag	100cc/hr = 1.0mg/hr x 1 infusion until complete	5.0mg
Bilateral PE	5	500cc total including r-tPA mixture x 2 bags	100cc/hr = 1.0mg/hr per infusion x 2 infusions (1 into each BEC) until complete	10.0mg

8.3.2 Reconstitution of r-tPA IV Infusion Mixture

a. Unilateral PE

- i. Obtain a 500cc bag of 0.9% NaCl for infusion.
- ii. Aspirate 5cc of 0.9% NaCl from the 500cc IV bag to have a total diluent of 495cc.
- iii. Mix three (3) vials (2.2ml injected into 2.2mg vials) of r-tPA with sterile water for injection until the lyophilized powder is dissolved, for a total of 6.6mg of r-tPA. (Do NOT use bacteriostatic water for injection).
- iv. Aspirate 5ml (5mg) into a syringe from vials.
- v. Verify 5ml are aspirated into the syringe.
- vi. Inject the 5mg solution of r-tPA into the IV bag for infusion. The IV bag has a total of 5mg of r-tPA in 500cc of diluent.

b. Bilateral PE

- i. Obtain two (2) 500cc bags of 0.9% NaCl for infusion.
- ii. Aspirate 5cc of 0.9% NaCl from each 500cc IV bag to have a total diluent of 495cc in each bag.

- iii. Mix five (5) vials (2.2ml injected into 2.2mg vials) of r-tPA with sterile water for injection until the lyophilized powder is dissolved, for a total of 10mg of r-tPA (1mg/ml).
- iv. Aspirate 5ml (5mg) dose into a syringe from vials.
- v. Verify 5ml are aspirated into the syringe.
- vi. Inject the 5mg solution of r-tPA into one IV bag for infusion. The IV bag has a total of 5mg of r-tPA in 500cc of diluent.
- vii. Repeat steps iv through vi for second IV bag.

9.0 BASHIR™ ENDOVASCULAR CATHETER INVESTIGATIONAL PROCEDURE

Please refer to the Instructions for Use for complete instructions on preparation, use, and handling of the Bashir™ and the Bashir™ S-B Endovascular Catheters (BECs).

9.1 Baseline Readings - Summary of Procedure Steps

1. It is recommended that the patient's blood pressure is under control prior to the investigational procedure.
2. Obtain venous access using ultrasound guidance and micropuncture needle. Ultrasound guidance and use of micropuncture needle is mandatory for both CFV and IJ access.
3. Place 7F sheath(s) in the RCFV or access point of choice (CFV or IJ). CFV or IJ access is operator's choice.

9.2 Choose one of the two anticoagulation options below according to the investigator's standard of care:

1. If heparin was administered pre-procedure or patient received LMWH >12 hours prior to the BEC procedure, start BEC procedure in the IR suite / cath lab while on heparin. Once r-tPA infusion is started, decrease dose of heparin to five (5) to eight (8) units/kg/hr up to a maximum of 1,000 units/hr.
2. If LMWH was administered \leq 12 pre-procedure, start BEC procedure without heparin in the IR suite / cath lab, until patient is eight (8) hours post last dose of LMWH. Then start dose of UFH at five (5) to eight (8) units/kg/hr up to a maximum of 1,000 units/hr. ACTs may be checked if standard of care.

9.3 Summary of Procedure Steps

1. Using a .035in exchange length wire, insert the wire into a sheath and advance it up to the right atrium.
2. Insert the Swan-Ganz or angled pigtail catheter over the wire and advance it up to the right atrium.
3. Remove the guidewire.
4. Float the Swan-Ganz catheter or angled pigtail into the pulmonary artery and record baseline hemodynamic data

5. Insert the exchange length guidewire, or equivalent, into the Swan-Ganz or angled pigtail catheter. Remove the Swan-Ganz or angled pigtail catheter.
6. Exchange the Swan-Ganz Catheter, or angled pigtail, for a long 7F or greater sheath (CFV access) or 7F sheath (IJ access) which is placed into the PA where the thrombus is located.
7. Remove the guidewire and the dilator carefully from the PA making sure that the sheath does not jump forward.

9.3.1 Intra-procedure Data Collection Requirements

1. Hemodynamic readings
2. AEs / SAEs
3. Times of pulse sprays administration
4. Time the r-tPA infusion(s) started
5. Time of heparin infusion(s) started
6. Technical complications
7. Medications (antiplatelet, anticoagulant, cardiac medications, and NSAIDs only)
8. Equipment used
9. Blood pressure and heart rate, at start of procedure

9.4 Bashir Endovascular Catheter Use – Procedure Steps

1. **Prepare all r-tPA solutions and IV infusion mixtures in Section 8.3** prior to opening the Bashir™ Endovascular Catheter (BECs). The Bashir™ S-B Endovascular Catheter may be preferred for smaller patients or for treatment of thrombus in the left pulmonary.
2. Prepare the relevant BEC(s) for use:
 - a. Ensure that the infusion basket of the BEC can be expanded and collapsed by moving the actuator on the handle backward and forward while depressing the white button.
 - b. With the basket expanded, flush the basket infusion port with standard flush solution. Observe for flush solution exiting the infusion holes of the basket. Collapse the basket.
 - c. Flush the wire lumen of the BEC observing that flush solution exits the tip of the catheter.
3. Using a .018in x 300cm length steel core non-hydrophilic guidewire, introduce the wire into the central lumen of the long sheath.
4. Backload the BEC onto the 0.018in guidewire and advance towards the long sheath. DO NOT insert the BEC into the sheath.
5. Attach a three-way stopcock to the infusion basket port of the BEC.
6. Commence r-tPA infusion via the stopcock on the basket infusion line connector using an infusion pump. Start the infusion through the BEC PRIOR TO inserting the catheter into the sheath. This is to maintain patency during catheter insertion, advancement, and positioning in the patient.

7. Advance the BEC into the target PA and retract the sheath to expose the basket segment.
8. Do NOT aspirate back from the basket infusion line connector to back bleed. Only maintain forward flow by infusing the r-tPA at the prescribed rate 100cc/hr for unilateral PE and bilateral PE, as stated in Table 2.
9. Keeping the wire in the central wire lumen expand the infusion basket of the BEC.

9.5 Pulse Spray of r-tPA for Unilateral and Bilateral PE

- a. **Unilateral PE:** With the catheter in the target PA, and after verifying that the basket portion of the catheter has exited the sheath under fluoroscopy, and with the guidewire in place, expand the basket of the catheter to the desired diameter making sure that the infusion limbs are expanded to less than the diameter of the vessel wall.
- b. Turn stopcock off to the infusion and administer 10ml (1.0mg r-tPA in 10ml) of pulse spray, from the 1st syringe of two syringes, into the thrombus at a steady rate over 10-15 seconds.
- c. Under fluoroscopy, with the guidewire in place, collapse the basket and re-expand the basket.
- d. Repeat this with the second 10cc syringe (1.0mg r-tPA in 10ml) over 10-15 seconds.
- e. As soon as the pulse sprays are administered, turn the stopcock open to the r-tPA infusion to restart the r-tPA via the infusion port of the BEC.

Please note: Even if the clot appears to be primarily unilateral, the default should be to use a second BEC in the contralateral pulmonary artery if there is any substantial clot on the contralateral side.

- f. **Bilateral PE:** Repeat, using a second BEC, steps a-e for bilateral PE.
- g. Once pulse sprays are complete, the basket(s) should remain expanded.
- h. Remove the guidewire(s), attach a 3-way stopcock and connect fluid or cap off the line. (See specifics at 9.9.3).

Please note that the BEC is to be placed in the optimal location to treat the PE. It is NOT to be used to selectively cannulate multiple branches of the pulmonary vasculature in multiple locations to administer the r-tPA.

9.6 r-tPA Infusion – Prior to Departing the IR Suite / Cath Lab

1. **For unilateral PE:** The total r-tPA infusion is 5mg at 1.0mg/hr. Using an IV pump at 100cc/hr, infuse the 500cc of 0.9% NaCl with the 5mg r-tPA at 1.0mg/hr until infusion is complete (approximately 5 hours).
2. **For bilateral PE:** The r-tPA infusion is 5mg at 1.0mg/hr into each BEC. Using two (2) IV pumps at 100cc/hr, infuse the 500cc of 0.9% NaCl x 2 simultaneously for 1.0mg/hr into each PE until complete (approximately 5 hours), for a total infusion dose of 10mg.

9.7 Anticoagulation Post-BEC Procedure

Heparin infusion at the completion of the BEC procedure and during the r-tPA infusion

1. Continue heparin administration through the side arm of the sheath at five (5) to eight (8) units/kg/hr up to a maximum of 1,000 units/hr. If bilateral BECs are in place, the heparin infusions must be administered into each sheath. Administer half (or approximately half) the dose prescribed by the investigator into the side arm of each sheath to equal the prescribed dose.
2. If subject has not reached 8hrs post last dose of LMWH in the IR suite / cath lab, then in the ICU start dose of UFH to five (5) to eight (8) units/kg/hr up to a maximum of 1,000 units/hr.

9.8 Maintaining Patency Through the Central Lumen of the BEC(s) During Transport to ICU

To maintain patency of the central lumen (guidewire lumen) of the BEC(s) during transport to the ICU, follow hospital standard protocol during transport to ICU, unless the BEC central lumen is not going to be used for PA pressure monitoring in the ICU and it is capped off.

9.9 Preparation in IR Suite / Cath Lab for Transfer to ICU

1. Suture sheaths in place.
2. Secure r-tPA and heparin drips to maintain infusions in the ICU.
3. The BEC central lumen (guidewire lumen) may be used to monitor PA pressures in the ICU.
 - a. Option #1: Connect fluid to central lumen (guidewire lumen) at hospital standard of care dose and rate (e.g. heparinized saline at 500 units/500cc .9% NaCl or 100 units/500cc .9% NaCl or .45% NaCl or other standard of care saline concentration, or normal saline without heparin) using pressure tubing to the stopcock to maintain patency until removal of the BEC(s). Using this set-up provides the option of monitoring the PA pressures in the ICU during the r-tPA infusion.
 - b. Option #2: If the central lumen of the BEC(s) is/are not going to be used for monitoring pressure in the ICU, the central lumen may be capped off prior to leaving the IR Suite / Cath Lab.
4. Securing the device(s):
 - a. For CFV Access: tape device to thigh. Then follow step "5" below.
 - b. For Right IJ Access: Cover the catheter with a sterile sleeve (such as the sleeve that comes with a Swan-Ganz catheter) tape device to left pectoral area with the shaft of the catheter placed posterior to the neck. Then follow step "5" below. Do the opposite for Left IJ access.
5. Place a strong adhesive dressing, such as Tegaderm™ (3M™, St Paul, MN) or equivalent tape over the handle and the actuator (slider) to make sure the handle and actuator (slider) are secure and cannot be moved.

6. For femoral access, a knee brace is recommended to prevent the patient from bending his/her knee when the BEC is in place.

10.0 POST-PROCEDURE PATIENT MANAGEMENT AND TESTS

The study subject will be admitted to the intensive care unit (ICU) where nursing staff are experienced in the care of patients treated for pulmonary embolisms.

10.1 r-tPA Infusion – Intensive Care Unit

1. **r-tPA Infusion:** Maintain the r-tPA Infusion through the infusion line on the side of the handle of the BEC in the ICU for approximately five (5) hours from start of the infusion in the IR suite / cath lab. The infusion should run at the rate prescribed in this protocol until the infusion is complete. *See section 8.3*

10.2 Post-r-tPA Infusion:

1. **Maintain BEC Infusion Basket Patency:** Once the r-tPA infusion is complete, maintain patency through the infusion basket of the BEC(s) by replacing r-tPA infusion with heparinized saline (per hospital standard of care e.g. 500 units/500cc .9% NaCl or 100 units/500cc .9% NaCl or other standard of care heparinized concentration) using an infusion pump, at 30cc/hr, until the BEC(s) is / are removed. Please note this solution must be heparinized.
2. **Anticoagulation Post-r-tPA infusion:** At the completion of r-tPA infusion, increase heparin dose to therapeutic doses with target aPTT in therapeutic range (suggested 60-80sec).
3. **Physical Exam:** A physical exam is required to be performed as soon as possible after the completion of the r-tPA infusion.

10.3 The Completion of r-tPA Infusion in the ICU

1. The BEC catheter(s) will be removed as soon as possible at the end of infusion only by an operator trained and approved to place and remove the study device. Collapse the basket(s) of the BEC(s).
2. Remove the BEC by retracting the catheter(s) carefully into the sheath(s) and then removing them from the body. Do not remove the sheath(s) at this time.
3. Please note: If pressurized tubing set-up was used to monitor the pressure through the central lumen of a BEC in the ICU, aseptically remove the tubing from the port at the back of the BEC and set aside for using for step 5a below.
4. Back bleed the sheath(s) and flush with heparinized saline.
5. Attach pressure tubing to the side arm of the sheath(s) and record the following:
 - a. Final hemodynamic parameters (PAS, PAD, PA Mean) – record from each PA if bilateral PE with bilateral sheaths in place.
 - b. S_pO_2 – Pulse oximetry oxygen saturation.
 - c. S_vO_2 – Mixed venous oxygen saturation.
 - d. CO – Calculate using the Modified Fick formula.

- e. CI – Calculate using the Modified Fick formula.
6. After BEC removal, the long sheath may be exchanged for a short sheath once the hemodynamic parameters have been recorded if the sheaths are not removed at the completion of the r-tPA infusion (after the effects of the r-tPA have worn off).

10.4 Sheath Removal

1. **Sheath removal:** Stop UFH for at least one (1) hour prior to sheath removal, unless the operator believes that the UFH, in the best interest of the patient, should not be stopped prior to and during sheath removal. Remove sheaths according to standard of care.
2. **Anticoagulation Post-Sheath Removal:** Re-start anticoagulation within one (1) hour post sheath removal with LMWH 1mg/kg SQ q12hrs or UFH at therapeutic doses for 24 hours post sheath removal. After 24 hours post sheath removal, physicians can start therapeutic anticoagulation according to their standard of care. If physicians choose to use DOACs then patients should be properly loaded according to the current guidelines.

11.0 TESTS REQUIRED 24 HOURS AFTER COMPLETION OF THE R-TPA INFUSION

11.1 Laboratory Tests and Other Tests

1. **BMP, CBC, Cardiac Biomarkers Troponin and BNP** – These tests will be drawn 24 hours (± 8 hours) after completion of the r-tPA infusion.

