6.2.2 Primary Safety Endpoint

Major bleeding, as defined by International Society of Thrombosis and Hemostasis (ISTH), within 72 hours of initiation of r-tPA infusion. ISTH major bleeding in non-surgical patients is defined as having a symptomatic presentation and:

- a. Fatal bleeding; and/or
- b. Symptomatic bleeding in a critical area or organ, such as intracranial, intraspinal, intraocular, retroperitoneal, intraarticular or pericardial, or intramuscular with compartment syndrome; and/or
- c. Bleeding causing a fall in hemoglobin level of 2.0g/dL (1.24mmol/L) or more or leading to transfusion of two or more units of whole blood or red cells.²⁷

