13.0 ASSESSMENTS REQUIRED 72 HOURS FOLLOWING START OF R-TPA INFUSION

13.1 Assessments

1. **AE/SAEs** – Adverse events will be monitored and reported on the CRF post-procedure through discharge.

Please note the primary safety endpoint assessment for bleeding within 72 hours will be assessed through 72 hours (-4 / +12 Hours) following initial administration of the r-tPA infusion in the IR suite / cath lab.

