13.2 Data Collection

1. **Medications** – All antiplatelet, anticoagulant, cardiac medications, and NSAIDs will be recorded that are administered within 72 hours following the infusion.
2. **If Subject has been discharged Prior to 72 Hour Visit** – If the study subject is discharged from the hospital prior to the 72-hour visit, the assessment may be conducted over the phone.
3. **COVID-19 Impact** - A COVID-19 Site Impact Assessment Form will be completed and submitted to the CRO prior to visits to be impacted by COVID-19.

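### The primary safety endpoint can turn on a 2.0 g/dL haemoglobin fall within 72 h, but no haemoglobin is required after about 21-37 h, so some late symptomatic bleeds cannot be graded reliably

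*Combined protocol and SAP*

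**What the plan says.** **Endpoint.** Section 6.2.2 defines the primary safety endpoint as ISTH major bleeding within 72 h of initiation of the r-tPA infusion. There is an entry condition ("ISTH major bleeding in non-surgical patients is defined as having a symptomatic presentation and"), followed by three alternatives: fatal bleeding, bleeding in a critical site, or criterion (c), "Bleeding causing a fall in hemoglobin level of 2.0g/dL (1.24mmol/L) or more or leading to transfusion of two or more units" of blood.

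**Haemoglobin schedule.** Section 7.1.1 requires a CBC within 48 h before the procedure. Section 11.1 requires one more, as part of the panel "BMP, CBC, Cardiac Biomarkers Troponin and BNP": "These tests will be drawn 24 hours (± 8 hours) after completion of the r-tPA infusion". Section 9.6 runs the infusion "until infusion is complete (approximately 5 hours"). The CBC row of Appendix 25.1 has the same two marks. Sections 12 to 15 require no later CBC.

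**72 h contact.** Section 13 covers adverse events and medications. Section 13.1 says that the bleeding endpoint "will be assessed through 72 hours (-4 / +12 Hours) following initial administration of the r-tPA infusion". Section 13.2 adds: "If the study subject is discharged from the hospital prior to the 72-hour visit, the assessment may be conducted over the phone". Footnote 6 of Appendix 25.1 describes that call as a check for adverse events and medication changes.

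**Test.** Section 20.2.4 sets a performance goal of 14.9% and an exact one-sided binomial test at 0.025. Section 20.3 analyses the endpoint in the ITT population, up to 125 subjects.

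**The concern.** Criterion (c) can be met by a measured fall alone, yet the plan requires no measurement over roughly the second half or more of the window. Anticoagulation continues through that period: heparin returns to the therapeutic range after the infusion (section 10.2), and anticoagulation restarts after sheath removal (section 10.4).

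Consider an access-site haematoma or haematuria that begins after the required CBC. If the site draws blood and finds a fall of 2.0 g/dL caused by the bleed, it is major. If the site does not, the same bleed is recorded as clinically relevant non-major or as an ordinary adverse event. Grading then depends on local practice at up to 20 sites and on time of discharge, although section 21.0 wants clinical events assessed uniformly.

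For this criterion an unmeasured fall can only lower the count. The trial has one arm and a fixed goal, so no concurrent control shares the loss. The ad hoc meeting trigger of eight major bleeds in the first 60 subjects (section 22.2.3) relies on the same ascertainment.

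**Working it through.** **1. The plan's own figure.** Section 20.2.4 gives 10% with a standard error of 2.45%. 0.10 + 2 × 0.0245 = 0.149, so the 14.9% goal reproduces. The issue is ascertainment, not the plan's arithmetic.

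**2. Time of the last required haemoglobin, from infusion start.** Inputs: infusion about 5 h (section 9.6); CBC at 24 ± 8 h after its end (section 11.1).
- Earliest: 5 + 16 = 21 h
- Nominal: 5 + 24 = 29 h
- Latest: 5 + 32 = 37 h

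These are approximate, because the 5 h is approximate and the infusion is interrupted for the pulse sprays.

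**3. Part of the window with no required value.** 72 − 37 = 35 h to 72 − 21 = 51 h (nominal 43 h). As clock time this is 35/72 = 49% to 51/72 = 71%. It is not the share of bleeds that fall there, which the documents do not give.

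**4. Which bleeds are exposed.** Going through section 6.2.2:
- Fatal bleeding, critical-site bleeding and transfusion of two or more units need no scheduled CBC.
- A haemoglobin fall without symptoms is not an event under the definition.
- What remains is a bleed that starts after the required CBC, is symptomatic, would qualify only by the haemoglobin fall, and has no unscheduled CBC.

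**5. Sensitivity of the test.** Let c be the largest count with P(X ≤ c | n, 0.149) ≤ 0.025. If the true rate is 0.149 and a fraction m of all major bleeds is missed, the chance of wrongly passing is P(X ≤ c | n, 0.149 × (1 − m)). The documents give no m, so every value below is an assumption. n = 125 is the enrolment maximum; n = 100 is a smaller treated set for comparison.

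| m (assumed) | Observed rate | n = 125, pass at ≤ 10 | n = 100, pass at ≤ 7 |
|---|---|---|---|
| 0 | 0.149 | 0.015 | 0.013 |
| 4% | 0.143 | 0.024 | 0.019 |
| 5% | 0.142 | 0.026 | 0.021 |
| 10% | 0.134 | 0.043 | 0.034 |

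The exact test is conservative at these sample sizes, so a loss of up to about 4% at n = 125 is absorbed within the nominal 0.025. At 5% it is just exceeded.

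**6. Effect of adding a CBC at the 48 h CTA.** The CTA is at 48 ± 8 h after the infusion ends (section 12.1): 5 + 40 = 45 h to 5 + 56 = 61 h from the start. The remainder is 72 − 61 = 11 h to 72 − 45 = 27 h, or 15% to 38% of the window.

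**The case against.** The strongest reply is that few bleeds are exposed and that other routes exist. The symptom requirement removes silent falls. The severe categories reach the sponsor through AE and SAE reporting. AEs are followed to discharge, with a physical examination in the 8 h before it (section 14.1), and are recorded again at 30 days (section 15.1). The AE definition includes abnormal laboratory findings (section 16.0), and the CEC/DSMB adjudicates. Many inpatients will have routine counts. All of this stands, and it makes the problem mainly one of grading rather than of bleeds going wholly unrecorded. It does not remove the problem: a phone call can establish that a haematoma occurred but cannot supply the haemoglobin change that decides its class, and adjudicators can use only values that exist.

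Two further cautions stand. The goal derives from SEATTLE II, and the documents do not describe that study's haemoglobin schedule, so a bias relative to the benchmark is not shown. The CRF is a separate document, and missing-data handling is referred to Section 8 of the SAP; neither was in the text reviewed, so local capture of haemoglobins may be better than the protocol implies.

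A reader might infer two stronger points that the documents do not support:
- **That 20-30% of major bleeds would be missed.** Reading the 49-71% of clock time as a share of events invites this. Nothing in the documents supports it, given how narrow the exposed group is.
- **That the −4/+12 h tolerance turns the endpoint into a 68 h or 84 h one.** Appendix 25.1 labels it a visit window, and the endpoint stays at 72 h in sections 6.2.2, 20.2.3 and 20.2.6. A bleed at 68-72 h can still be recorded at discharge or at 30 days, and counting events to 84 h would work against passing. Only an explicit onset-time rule is lacking.

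**Conclusion.** The gap is real. Criterion (c) covers 72 h, the last required haemoglobin is at about 21-37 h, and nothing later is required. For late symptomatic bleeds that would qualify by haemoglobin fall alone, the grade depends on whether the site chose to draw blood, and the resulting error lowers the major-bleeding count.

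The size is unknown and probably modest, since only a minority of major bleeds is likely to be exposed. If the true rate equals the goal, the n = 125 test holds its 0.025 level up to about 4% missed, and n = 100 still holds it at 5%. At 10% the level is 0.043 or 0.034. Confidence is high in the schedule gap and low in its numerical effect. It is worth correcting because the remedy is cheap and a value that was never drawn cannot be recovered later.

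**What to change.** 1. Add a CBC to the 48 h (± 8 h) CTA visit in section 12 and to the CBC row of Appendix 25.1.
2. Record on the CRF every locally drawn haemoglobin through 72 h from infusion start, including any drawn because of a reported bleed.
3. Have the CEC grade criterion (c) on the fall from the last pre-procedure value to the lowest value through 72 h, only where a symptomatic bleed is judged to have caused the fall. Without that link a lowest-value rule could count dilution, since subjects receive 500 to 1,000 cc of infusate (Table 2).
4. State in sections 13.1 and 20.2.3 that events count by onset time up to 72 h from infusion start, whatever the date of the visit.

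**Cost.** One routine blood count per subject at a visit already required for the contrast CTA, plus CRF and protocol wording. The observed major-bleeding rate may rise slightly. The last 11-27 h still has no required value; item 2 narrows that gap but does not close it.
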